#### Injection and sexual risk-taking behavior

Injection and sexual risk-taking behaviors will be measured by the survey performed at baseline and then at follow-up visits.

#### Reasons PWID choose to initiate and discontinue PrEP

The baseline and follow-up surveys will assess the main reasons for agreeing to start PrEP and stopping it (if stopped during the study period). The quantitative data will be supplemented by acquiring information about core reasons for initiating or refusing PrEP, based on the individual interview qualitative data from participants.

#### Incident HIV-seroconversions and characteristics

HIV testing will be performed with confirmation if necessary at all study visits.

#### Adverse events

Measurement of AEs will be graded via the DAIDS Toxicity Grading System determined by review of reported adverse events (clinical and laboratory) during the study.

## 7.2 Sample Size Consideration

A total sample size of 200 PWID participants will be recruited into the study. Each participant will be enrolled to receive daily PrEP with Navigation for at least 6 months. Half of them will be randomized to receive SMS reminders.

For the PrEP adherence endpoint, the adjacent table lists the two-sided 95% confidence intervals for the true percentage of the PrEP adherence rates for the PWID who actually receive PrEP, assuming a 10% to 20% loss-to-follow-up (e.g. including those lost due to incarceration) during the 6-month period. For example, if the PrEP acceptance rate is 50% and an observed adherence rate is 67%, then there is 95% chance that the range 58%-76% will contain the true PrEP adherence rate.

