## 2.0 STUDY OBJECTIVES AND DESIGN

### 2.1 Primary Objectives

- To compare adherence to and retention on daily PrEP prescribed as the fixed dose formulation to PWID randomized 1:1 to PrEP as usual or SMS-enhanced PrEP.

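### The only sample-size justification is the precision of one adherence rate pooled over both arms: it says nothing about the SMS-versus-control comparison, and its intervals are printed slightly too narrow

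*Protocol*

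**What the plan says.** Section 7.2 of the protocol fixes the size: "A total sample size of 200 PWID participants will be recruited into the study", and "Half of them will be randomized to receive SMS reminders". It then says that "the adjacent table lists the two-sided 95% confidence intervals for the true percentage of the PrEP adherence rates". The denominator of these intervals is limited to those taking the drug ("for the PWID who actually receive PrEP"), and between 10% and 20% of participants are taken to be lost over the six months. The table crosses a PrEP rate of 33%, 50% or 67% with an adherence rate of 33%, 50% or 67% and a loss of 10% or 20%, giving 18 intervals. The example in the text reads "if the PrEP acceptance rate is 50% and an observed adherence rate is 67%, then there is 95% chance that the range 58%-76" per cent contains the true adherence rate. This is the cell for a 50% PrEP rate, 67% adherence and 10% loss. The text calls the row factor acceptance, while the table heads it persistence.

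Section 2.1 gives the primary objective as "To compare adherence to and retention on daily PrEP" between participants randomised 1:1 to PrEP as usual or SMS-enhanced PrEP. The primary adherence model in section 7.3.1 is a GEE with terms for arm, time and their interaction.

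**The concern.** The protocol chose to justify its sample size, but the justification answers a different question from its primary objective. The precision of one overall adherence rate does not show how well 100 participants per arm can separate SMS from control. Section 7.2 gives no effect size, power, detectable difference or interval for a difference. Someone deciding whether 200 is enough, or later reading an inconclusive result, has only a table of intervals about half as wide as those for the comparison.

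The printed intervals also do not reproduce with ordinary rounding at the stated 200, and every one errs in the favourable direction. The error is small, but these are the only error bars in the plan. The row factor sets the denominator of every cell and carries two names. Section 7.1 defines persistence as a time from start to discontinuation, which is neither an acceptance rate nor a percentage.

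**Working it through.** **Inputs, all from section 7.2.** N = 200; half randomised to SMS, so 100 per arm; two-sided 95%, z = 1.96; loss 10% or 20%; PrEP rate 33%, 50% or 67%; adherence p = 33%, 50% or 67%.

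**Step 1: the worked example.** Pooling both arms, n = 200 × 0.90 × 0.50 = 90. The Wald half-width is 1.96 × √(0.67 × 0.33 / 90) = 9.71 points, so the interval is 57.3% to 76.7%. Ordinary rounding gives 57%-77%. Cutting the half-width down to 9 gives the printed 58%-76%.

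**Step 2: the whole table.** The formula is p ± 1.96 × √(p(1 − p)/n), with n = 200 × (1 − loss) × PrEP rate.

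- With ordinary rounding, 7 of the 18 printed intervals match.
- With both limits rounded inward, 17 of the 18 match.
- All 18 printed half-widths are below the computed ones. The smallest gap is 0.30 points (50% PrEP rate, 67% adherence, 20% loss: 10.30 computed, 10 printed). The largest is 0.96 points (33% rate, 33% or 67% adherence, 10% loss: 11.96 computed, 11 printed). Relative to the computed half-width, the gap runs from about 3% (0.30/10.30) to about 10% (0.92/8.92, at a 67% rate, 50% adherence, 10% loss).
- The one remaining cell (50% rate, 50% adherence, 20% loss) has n = 80 and computes to 39.04% to 60.96%. It is printed as (39%, 60%). That is not symmetric about 50%, so no sample size yields it with symmetric rounding. Its shortfall lies wholly at the upper limit, and its average half-width is 10.5 against 10.96.

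**Step 3: the arm difference on the table's own denominator.** If the n analysed participants split evenly, each arm has n/2. The half-width for a difference of two proportions near p is 1.96 × √(2p(1 − p)/(n/2)) = 2 × 1.96 × √(p(1 − p)/n), exactly twice the pooled value.

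- 50% rate, 67% adherence, 10% loss: 45 per arm, 1.96 × √(2 × 0.67 × 0.33 / 45) = ±19.4 points (printed pooled ±9).
- Same, 20% loss: 40 per arm, ±20.6 points (printed pooled ±10).
- 33% rate, 50% adherence: 29.7 per arm at 10% loss, ±25.4 points; 26.4 per arm at 20% loss, ±27.0 points (printed pooled ±12 and ±13).

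**Step 4: the arm difference if all randomised participants are analysed.** Per arm, 100 × 0.90 = 90 or 100 × 0.80 = 80. At 50% adherence, 1.96 × √(2 × 0.25 / 90) = ±14.6 points and 1.96 × √(2 × 0.25 / 80) = ±15.5 points.

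**The case against.** The strongest reply is that the table does what it says. Text and title both describe intervals for a true adherence rate, and neither claims to give the precision of an arm difference. A single-rate interval also suits part of the stated purpose: the Schema and section 7.1 speak of acceptability and feasibility. This stands as far as it goes. The pooled interval is a legitimate calculation, and the protocol does not present ±9 points as the precision of the primary answer. A reader might infer that, but the text does not say it. What remains is that the comparison named as primary has no justification at all.

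A reader who tries to reproduce the table might also infer that it was computed for a larger study, because totals from 221 to 232 with ordinary rounding match 17 of the 18 cells. The documents do not support this. The stated 200 with inward rounding matches the same number of cells, as does every total from 199 to 212, and the protocol gives 200 consistently.

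The between-arm figures rest on choices that the protocol does not make. Section 7.3.1 does not say whether the GEE is limited to those taking PrEP, so the ±19 to ±27 range applies only if it is. The all-randomised figures fit a randomised comparison better. This is fair, and both sets are given with their conditions.

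The rounding error alone, under one point per side, changes no decision. That is also fair, and it is the minor part of this point.

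**Conclusion.** The point holds. Section 7.2 justifies 200 participants only by the precision of a pooled single rate, while sections 2.1 and 7.3.1 make the randomised comparison primary. The plan gives no precision for that comparison.

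The size depends on who is analysed. With all randomised participants after 10-20% loss, the half-width is about ±14.6 to ±15.5 points at 50% adherence. With PrEP users only, split evenly by arm, it is about ±19.4 to ±20.6 points at a 50% rate and 67% adherence, and about ±25 to ±27 points at a 33% rate and 50% adherence. These are unadjusted Wald figures for one time point with similar adherence in both arms. The GEE over months 3 and 6 may differ somewhat.

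The secondary arithmetic point also holds, in a small form. Every printed interval is narrower than 200 participants give, by 0.30 to 0.96 points in half-width. Inward rounding explains 17 of the 18 cells, and the other has one wrong digit. Nothing here shows that the sample size is wrong or that the table came from another study.

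**What to change.** Keep 200 participants and revise section 7.2 in four ways.

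1. Reprint the table with ordinary rounding:

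| PrEP rate | Adherence | 10% loss | 20% loss |
|---|---|---|---|
| 33% | 33% | (21%, 45%) | (20%, 46%) |
| 33% | 50% | (37%, 63%) | (37%, 63%) |
| 33% | 67% | (55%, 79%) | (54%, 80%) |
| 50% | 33% | (23%, 43%) | (23%, 43%) |
| 50% | 50% | (40%, 60%) | (39%, 61%) |
| 50% | 67% | (57%, 77%) | (57%, 77%) |
| 67% | 33% | (25%, 41%) | (24%, 42%) |
| 67% | 50% | (41%, 59%) | (41%, 59%) |
| 67% | 67% | (59%, 75%) | (58%, 76%) |

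2. Change the worked example to 57%-77%, and say that these intervals pool both arms.

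3. Use one name for the row factor in text and table, distinct from the time-based persistence endpoint in section 7.1 unless that is what is meant.

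4. Add the 95% half-width of the SMS-minus-control difference. State which participants it covers, the loss, the adherence level and that the arms are of equal size, using the ranges above.

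The cost is protocol wording only. The downside is that the stated precision becomes less favourable, slightly so for the pooled rate and clearly so once the comparison is shown.

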**Table: 95% Confidence Intervals for the True PrEP Adherence Rate Given by Possibly Observed PrEP Adherence Percentages**

PrEP Persistence Rate	PrEP Adherence Rate	95% CI for True PrEP Adherence Rate	
		10% LTFP*	20%LTFP*
33% (low)	33%	(22%, 44%)	(21%, 45%)
	50%	(38%, 62%)	(37%, 63%)
	67%	(56%, 78%)	(55%,79%)
	33%	(24%, 42%)	(23%, 43%)
	50%	(40%, 60%)	(39%, 60%)

50% (moderate)	67%	(58%, 76%)	(57%,77%)
	33%	(25%, 41%)	(25%,41%)
67% (optimistic)	50%	(42%, 58%)	(41%,59%)
	67%	(59%, 75%)	(59%.75%)

\*LTFP: Loss-to-Follow-up

## 7.3 Data Analysis

### 7.3.1 Primary Analyses

#### *PrEP adherence*

For binary outcome of high levels of PrEP adherence (defined as TDF  $\geq$ 700 fmol/punch), generalized estimating equation models (GEE) with binomial distribution will be built to account for correlation in repeated measurements occurring in the same participant. Intervention assignment, time, interaction between time and intervention assignment and any other confounders will be included as covariates. The analysis will be done for repeated measure for both 3 and 6 months. As an alternative analytical plan for assessing the impact of the two intervention arms on adherence to PrEP, continuous version of adherence will be analyzed by using repeated-measures analysis with same set of covariates as the binary outcome and percent change in adherence between different assessment points will be estimated and compared between intervention assignment using linear contrast statement in SAS PROC MIXED. For the above mentioned model, Covariance structure will be selected based on the fit statistics (i.e., AIC, BIC etc.).

There are several strategies by which the PrEP adherence will be measured. We will utilize Spearman correlation coefficients, scatterplots and Kappa statistics to assess associations between the biomedical (TDF concentrations in red blood cells measured via DBS) and self-report measures (VAS: visual analogue scale and 3-item assessment).

#### *PrEP persistence*

Kaplan-Meier plots will be used to characterize time to first discontinuation, as well as time to restarting PrEP among discontinuers, both overall and by age, education, and risk group. Intervention assignment, time, interaction between time and intervention assignment and any other confounders will be included as covariates. Among those continuing on PrEP, we will consider the medication possession ratio, defined as the number of tablets dispensed divided by the number of days between visits, a measure that performed best as an indicator of drug exposure in the iPrEx study.

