## Implementation of HIV Pre-Exposure Prophylaxis (PrEP) among People Who Inject Drugs (PWID) in Ukraine

### SCHEMA

Purpose:	To assess the acceptability and feasibility of PrEP for People Who Inject Drugs (PWID) in Kyiv, Ukraine with and without SMS facilitation.
Design:	An 24-week prospective randomized controlled trial of PrEP as usual versus PrEP with SMS facilitation
Population:	HIV-uninfected PWID at risk for HIV infection in Kyiv, Ukraine.
Study Size:	A total of 200 participants randomized 1:1 to experimental and control arms.
Study Regimen:	All participants will be offered once daily oral emtricitabine 200 mg / tenofovir disoproxil fumarate 300 mg (FTC/TDF) combined with SMS facilitation in the experimental arm.
Study Duration:	12 months including closeout activities. Preparatory phase is planned to take 2 months. Recruitment is anticipated to take place over a 2-month period. Each participant will be followed for a total of 6 months. Two months are included for data clean-up and closeout.
Primary Objectives:	To compare adherence to and persistence on daily PrEP prescribed as the fixed dose formulation to PWID randomized 1:1 to PrEP as usual or SMS-enhanced PrEP.
Secondary Objectives:	

 To describe patterns and attributes of PrEP adherence among participants (e.g., SMS intervention acceptance, substance use, sociocultural factors)

 To measure changes in injection and sexual risk taking behavior among study participants

 To describe client- and provider-level barriers to PrEP initiation and adherence

Study Sites:	

 Institute of Epidemiology and Infectious Diseases (Lavra) Clinic

 Club Eney Community Center

---

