### 5.3 Month 1, 3 and Month 6 (exit visit)

At months 1 and 3, the participants will visit the clinical site to complete the assessments and receive the medication supply for next two (at month 1) three (at month 3) months. At month 6, participants will not receive medication as a part of the study, but will be referred to other available PrEP providers in Kyiv. The following procedures will be included.

- Verify locator information
- Behavioral and psychosocial survey
- Self-reported study product adherence assessment
- PrEP discussion
- PrEP Navigation and study product supply
- Autonomy supportive adherence counseling
- SMS reminder customization

- HIV/ STI behavioral risk-reduction counseling, provision of prevention supplies
- Medical history including but not limited to co-morbidities, concomitant medications, HIV risk history
- Symptom-driven physical exam
- AE Assessment
- HIV rapid test – at months 3 and 6.
- DBS storage for pharmacology testing
- Urine storage for substance use testing

The exit visit will include all procedures for Month 3, except for PrEP provision and related counseling and SMS customization.

#### 5.4 Months 2, 4, 5

Monthly assessments between the PrEP dispensing visits (Enrollment and 3-month) will be conducted by research staff **by telephone**. The following procedures will be included.

- Review and update locator information
- Self-reported study product adherence assessment

Self-reported PrEP adherence for all participants will be assessed using both a visual analogue scale (VAS) and a new 3-item self-report measure. The VAS is empirically validated, consistently under-reports adherence, but effectively measures a “difference” in adherence that changes in response to an intervention. The 3-item adherence self-report scale showed good psychometric characteristics and good construct validity when compared with an drug monitoring standard. Two self-report adherence measures are often recommended.

- PrEP discussion
- Autonomy supportive adherence counseling
- SMS reminder customization

Experimental arm participants will have an opportunity to change the parameters of the SMS reminders.

- HIV/ STI behavioral risk-reduction counseling

After the standard risk-reduction counseling, the participants will be invited to visit the harm reduction site to receive supplies.

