#### PrEP persistence

PrEP persistence is defined as the time from PrEP start to PrEP discontinuation. A PrEP discontinuation is considered to have occurred if a participant self-reported to miss the PrEP doses for 30 or more consecutive days, for reasons other than a medication hold instituted by a clinician.

**Secondary Endpoints:** The secondary endpoints of this study include the following:

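### Persistence is to be compared between arms, but the persistence analysis as written specifies no valid arm comparison, and its possession ratio mainly reflects visit timing

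*Protocol*

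**What the plan says.** The Schema gives the primary objective as "To compare adherence to and persistence on daily PrEP prescribed as the fixed dose formulation to PWID randomized 1:1"; the two arms are usual PrEP and PrEP with SMS reminders. Section 2.1 repeats it with retention in place of persistence. The Schema sets the size: "A total of 200 participants randomized 1:1 to experimental and control arms".

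Section 7.1 defines the endpoint: "PrEP persistence is defined as the time from PrEP start to PrEP discontinuation". A discontinuation counts when the participant has "self-reported to miss the PrEP doses for 30 or more consecutive days", unless a clinician instituted the hold.

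Section 7.3.1, under the primary analyses, plans Kaplan-Meier plots of time to first discontinuation and "time to restarting PrEP among discontinuers, both overall and by age, education, and risk group". The next sentence reads "Intervention assignment, time, interaction between time and intervention assignment and any other confounders will be included as covariates". The section then adds, for those still on PrEP, a medication possession ratio "defined as the number of tablets dispensed divided by the number of days between visits".

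On supply, section 5.2 (item 9) provides one month of tablets at enrolment. Under section 5.3, participants at the next two clinic visits "receive the medication supply for next two (at month 1) three (at month 3) months", and nothing is dispensed at month 6.

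**The concern.** Three features of the persistence analysis work against a comparison of SMS with control.

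- **Strata and covariates.** The curves are split by baseline characteristics and not by the randomised factor. The covariate sentence that could bring arm back in repeats the sentence written for the GEE model of adherence earlier in section 7.3.1. Here it follows a descriptive plot.
- **Event definition.** A stop is seen only if the participant reports it. Someone who leaves care and stops taking PrEP reports nothing and is censored. Reminders might act partly by keeping people in contact, so loss and stopping may be linked, and linked differently in each arm.
- **Possession ratio.** The quantity of tablets is set to match the interval it covers, and only continuers are counted.

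The trial is open-label. If the protocol text is followed, the test for a stated primary comparison is left to be chosen later, and the censoring implied by the definition can bias it.

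**Working it through.** The protocol states no effect size, event count or power for persistence, so there is no planned figure to reproduce. The check is a reading of the text plus arithmetic.

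**1. Arm comparison.** The Schema asks for a contrast between arms. The listed Kaplan-Meier groupings are overall, age, education and risk group. A Kaplan-Meier curve is stratified and takes no covariates, so the covariate sentence needs a hazard model to be meaningful. Section 7.3.1 attaches none to it.

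**2. Censoring of losses.** The loss of 10% to 20% over six months comes from section 7.2. The following are my assumptions: 100 starters in one arm, 5 reported stops per month for six months (30 in all), and losses L spread evenly and removed after each month's stops.

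Kaplan-Meier: S(6) = product over months of (1 − 5/n), where n falls each month by 5 + L/6.

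- L = 10: n = 100, 93.3, 86.7, 80, 73.3, 66.7, giving S(6) = 0.685.
- L = 20: n = 100, 91.7, 83.3, 75, 66.7, 58.3, giving S(6) = 0.666.

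If a share f of those lost had in fact stopped, true persistence is 0.70 − f × L/100.

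| f | True, L = 10 | Kaplan-Meier | True, L = 20 | Kaplan-Meier |
|---|---|---|---|---|
| 0 | 0.70 | 0.685 | 0.70 | 0.666 |
| 0.5 | 0.65 | 0.685 | 0.60 | 0.666 |
| 1 | 0.60 | 0.685 | 0.50 | 0.666 |

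Under these assumptions the error runs from a slight understatement (0.685 against 0.70, and 0.666 against 0.70) to an overstatement of 0.685 − 0.60 = 0.085 or 0.666 − 0.50 = 0.166. The direction and size depend on f, which the documents do not give.

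**3. Possession ratio.** Assume 30-day months and one tablet daily, so supplies are 30, 60 and 90 tablets. Ratio = tablets / (tablets + days late).

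| Visit timing | After 30 tablets | After 60 | After 90 |
|---|---|---|---|
| 7 days early | 1.30 | 1.13 | 1.08 |
| On time | 1.00 | 1.00 | 1.00 |
| 7 days late | 0.81 | 0.90 | 0.93 |
| 14 days late | 0.68 | 0.81 | 0.87 |
| 30 days late | 0.50 | 0.67 | 0.75 |

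A visit 15 days late after the 60-day supply gives 60/75 = 0.80. With full supply, an on-time attender scores 1.00 in either arm whatever number of tablets is taken.

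**4. The same tablets over fixed follow-up.** Dividing by 180 days in all randomised gives 180/180 = 1.00 for full supply, (30 + 60)/180 = 0.50 for someone who collects only the first two supplies, and 30/180 = 0.17 for the first only. Those who stop collecting are then counted; the ratio in section 7.3.1 leaves out anyone no longer continuing.

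**The case against.** The strongest reply is that section 7.3.1 does state an intention to include intervention assignment. A reader might infer from the strata that SMS cannot be compared with control at all. The text does not support that: events are collected in both arms, curves by arm remain possible, and a statistical analysis plan not shown here could name the model. The absence of a named model is therefore not the point by itself. What stands is that the protocol fixes strata without arm and joins a covariate list to a method that cannot use it.

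It would also be wrong to say that time can never be a covariate for a time-to-event outcome. A discrete-time hazard model uses time, and an arm-by-time term allows non-proportional hazards. With monthly assessments that is a sensible reading, but it is not what is written.

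On censoring, putting 10% loss in one arm and 20% in the other in the illustration above, with every lost participant having stopped, would shrink a true 10-point difference to about 2 points (0.685 against 0.666). The documents do not support that as an estimate: section 7.2 gives a planning range for overall loss, not a contrast between arms. It also counts incarceration as loss, and section 1.1 reports that incarceration went with higher adherence in an earlier trial, so loss need not mean stopping. Monthly assessments, including telephone contacts (section 5.4), and in-person tracing (section 3.4) should also reduce unreported stops.

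On the ratio, it is not strictly constant: visit timing, refused supply and supply at interim visits (Appendix I) move it. It is supplementary, and the protocol cites its performance in an earlier trial, which cannot be checked here. Drug exposure is measured separately by dried blood spot. None of this changes the arithmetic for on-time attenders.

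Finally, section 7.1 names adherence as the primary endpoint, and adherence has its own arm-based GEE. To say that half of the primary objective is lost would go too far.

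**Conclusion.** The point holds in this form. The Schema requires a comparison of persistence between arms, and section 7.3.1 as written does not specify a valid one. Censoring of losses overstates persistence to the extent that those lost have stopped, and can hide an arm difference if loss differs by arm. The size is unknown; the figures above rest on assumed stops and an assumed share of stoppers among those lost, and show only the possible range. The possession ratio is largely set by the dispensing schedule, reflects visit timing, and conditions on continuing after randomisation, so it is weak evidence on SMS.

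A reader might also infer that measuring from PrEP start is an error, because participants may abstain or start later (sections 5.2 and 4.2) and never-starters have no start date. That is the protocol's explicit definition, and the number of never-starters is not given. Counting them as events at day 0 would change the endpoint to uptake plus persistence, so it belongs in a supplementary analysis.

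**What to change.** Amend the persistence text in section 7.3.1, before outcomes are examined by arm, as follows.

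1. Plot Kaplan-Meier curves by randomised arm. Test with a log-rank test stratified by site, the randomisation stratum in section 5.2, and report a Cox hazard ratio stratified by site. Keep the curves by age, education and risk group as descriptive. Either delete the covariate sentence or attach it to a named hazard model.
2. Count a participant lost with no further supply as discontinued when the last dispensed supply runs out. Give the analysis that censors at last contact as the sensitivity analysis.
3. Replace the possession ratio with tablets dispensed over fixed follow-up days in all randomised participants, labelled as a measure of supply and not of drug taking.
4. Add a supplementary intention-to-treat analysis from randomisation with never-starters as events, and state how late starters are handled.

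The cost is analysis wording, using dispensing and visit dates that the study should already hold. The downside of item 2 is that some lost participants who obtained drug elsewhere are counted as stopped; the sensitivity analysis shows how much the result depends on the rule.
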